1. PREVIOUS STUDY HISTORY

Has this study ever been reviewed and rejected/disapproved by another IRB prior to submission to this IRB?

No Yes – if yes, please explain: |

2. BRIEF SUMMARY OF RESEARCH

- *The summary should be written in language intelligible to a moderately educated, non-scientific layperson.*
- *It should contain a clear statement of the rationale and hypothesis of your study, a concise description of the methodology, with an emphasis on what will happen to the subjects, and a discussion of the results.*
- *This section should be ½ page*

This is a multi-center prospective randomized clinical trial examining how IRIS (Intelligent Real-time Image Segmentation) affects biopsy patterns in VLE (Volumetric laser endomicroscopy). Patients will undergo a VLE exam with and without IRIS per the standard of care. All patients regardless of the study participation in this study would receive VLE with and without IRIS clinically. Thus randomization into a particular order will not require more procedure time. They will be randomized into VLE without IRIS first vs VLE with IRIS first. The BUDDY Randomization System provided for use by the Northwell Health Biostatistics Unit will be used for this. Randomization will occur before the procedure starts. Randomization will be stratified based on prior diagnosis of dysplasia. The order the patient is randomized to will be recorded on the case report form. There will be concealed allocation as the study coordinator performing the randomization will not know the order of the next allocation.

Both VLE and IRIS imaging are being performed as standard of care. However, randomization of the order allows for comparison of the two. Regions of interest (ROI) will be recorded using a full scan and recorded on the case report form. The time to identification of ROIs will also be recorded. Each group will then cross over such that the VLE without IRIS group will then have IRIS turned on ROI will

then be recorded for each group based on full scans. A consensus ROI will be recorded based on the two exams. Only one ROI per centimeter will be allowed to avoid overlapping of laser marks. In addition VLE without IRIS and IRIS marks within 75 frames of each other or 2 hours (on a clock face orientation) will be considered the same target.

Laser marking will then be performed. A double laser mark will be applied to all IRIS ROIs. A single laser mark will be applied to VLE ROIs. Targeted biopsies will be taken of all laser marks and placed in separate biopsy jars. Biopsies will be taken in between the laser marks for double laser marked areas. For single laser marks, biopsies will be taken on either side of the laser mark. Resection of visible lesions will then occur per standard of care (if present) followed by random biopsies of the segment. Random biopsies are pinch biopsies every 1 cm the length of the Barrett's in a 4 quadrant fashion per gastrointestinal society guidelines. There are no additional research biopsies being performed outside this study. The targeted biopsies are based on the VLE features that are suspicious for dysplasia and thus standard of care. The other biopsies being performed here are random biopsies which are also being performed for standard of care. Biopsied samples will be stored per standard of care procedures per the pathology department. They will not be stored for future research purposes.

Following each procedure, the physician will be asked a series of Likert Scale questions (see post-protocol survey in case report form) to assess the utility of IRIS in that procedure, including how it impacts their confidence in image interpretation, their ability to assimilate data more easily and quickly, and their overall perception of the technology.

Although, the VLE with IRIS and VLE without IRIS are being performed as standard of care, all adverse events will be recorded and reported to the IRB.

All data will be entered into a central encrypted REDCap database.

Expert pathologists who specialize in gastrointestinal pathology will read the histology. A second gastrointestinal pathologist will confirm any histologic diagnosis of dysplasia. This is the standard of care at Northwell Health and academic medical centers per gastrointestinal society guidelines.

All procedures (upper endoscopy, volumetric laser endomicroscopy, and IRIS enhanced VLE) will be performed as standard of care. The prospective data collection and initial randomization will be the research component. All data collected will be de-identified before being transferred into a database. This will be kept in a safe place that is only accessible to the research team.

.

3. INTRODUCTION/BACKGROUND MATERIAL/PRELIMINARY STUDIES AND SIGNIFICANCE

- *Describe and provide the results of previous work by yourself or others, including animal studies, laboratory studies, pilot studies, pre-clinical and/or clinical studies involving the compound or device to be studied.*
- *Include information as to why you are conducting the study and how the study differs from what has been previously researched, including what the knowledge gaps are.*
- *Describe the importance of the knowledge expected to result*

Barrett's esophagus (BE) is a change from normal esophageal squamous epithelium to specialized intestinal metaplasia.[1] It is estimated that 5.6% of adults in the United States have BE.[2] BE is a major risk factor for esophageal adenocarcinoma (EAC), the incidence of which continues to rise.[3] Interventions to impact the increasing incidence of EAC are limited due to two factors: 1) many patients with BE may remain undiagnosed until a symptomatic cancer arises;[4] and 2) traditional surveillance approaches are imperfect at identifying which BE patients will progress to cancer.[5]

Currently, cancer risk stratification in BE is based upon the detection of dysplasia in random biopsies taken every 1-2 cm over the length of the BE.[1,6] However,

detecting and appropriately classifying dysplasia can be difficult. Dysplasia may be focal, and most biopsy techniques sample a fraction of the BE.[7] Moreover, endoscopic surveillance of patients with known BE may not improve mortality from EAC,[5] though it is associated with increased cost. Thus, current needs in the evaluation of BE include improvements in screening approaches and the ability to detect dysplasia.

Volumetric laser endomicroscopy (VLE) procedures use an advanced imaging technology that became commercially available in the United States in 2013 (NvisionVLE® imaging System, NinePoint Medical Inc., Bedford, MA). The VLE procedure uses an FDA-cleared second-generation optical coherence tomography (OCT) technology. It uses infrared light to produce real time high-resolution cross sectional imaging of the esophagus. The NvisionVLE system can scan a 6 cm length of the esophagus in approximately 90 seconds, providing surface and subsurface wide-field cross-sectional imaging with an axial resolution of 7 μ m, and to a depth of 3 mm.[8,9] The VLE imaging system consists of a console, monitor, and optical probe contained within a Mylar balloon on an 8Fr, 260 cm catheter. The distal end of the catheter connects to the console. The probe is available in 14 mm, 17 mm, and 20 mm diameter balloons that are 6 cm in length. The balloon is positioned such that the distal margin of the balloon is located 1 cm distal to the gastroesophageal junction. This allows a single scan to image the gastric cardia, the gastro-esophageal (GE) junction, and the distal esophagus. The balloon is inflated to 15 psi, though depending on anatomy the balloon inflation pressure may be modified accordingly. The inflated balloon allows for centering and anchoring of the probe while helical scanning occurs. Imaging is performed during automatic retraction of the probe from the distal to proximal end of the balloon over a 90 second period, creating real time 360-degree images. Twelve hundred cross sectional scans are generated over the 6 cm segment. VLE scans are viewed by using a software interface that allows real time viewing of cross-sectional, transverse, and longitudinal views. There is a registration line on the balloon and

the VLE images that allows for orientation of VLE images with endoscopic imaging.

A recent upgrade to the imaging platform includes the ability to perform superficial laser marking of the esophageal epithelium when suspicious areas are identified on VLE to provide more precise targeting for biopsies or endoscopic resection .[10] A safety and efficacy study was performed evaluating VLE with a prototype laser marking device in 16 BE patients with 222 laser marks placed.[11] The study showed that laser marking was safe and efficacious with an 85% positional accuracy rate of the laser marks.

Scoring systems for OCT and VLE images have been developed to help detect neoplasia (HGD and intramucosal cancer) in BE.[12,13] These scoring systems were developed by VLE scanning *ex vivo* endoscopic resection specimens and correlating VLE features to histology.[14–16] A potential advantage of VLE is its ability to detect subepithelial disease in BE,[16–18] though the clinical relevance of these findings remains uncertain.[19]

Multiple case reports and case series have demonstrated the potential of VLE to identify dysplasia in BE not detected by high-definition white light endoscopy or electronic chromoendoscopy.[14–16,20] A large single center retrospective series found an incremental yield of dysplasia detection using VLE with laser marking compared to VLE without laser marking or random biopsies.[21] A study looked at the interobserver agreement between users at high-volume academic centers based on still images and found strong agreement for non-neoplastic and neoplastic BE (kappa 0.66 and 0.79).[22] Although the learning curve for interpretation of VLE images appears to be favorable,[23] a large amount of complex data is interpreted by the endoscopist in real-time. Thus, computer-aided analysis of VLE data could aid in image interpretation mid-procedure. [12, 13, 24] One academic group has developed computer algorithms to aid with the detection of BE neoplasia, evaluating a prototype computer-aided detection program using 60 VLE images of

ex vivo endoscopic resection specimens.[25] The study found that the computer-aided detection was able to detect neoplasia with a 90% sensitivity and 93% specificity. An artificial intelligence algorithm to segment and display commonly observed esophageal features [12, 13, 24] has been commercially developed, and is cleared by the FDA. This product is termed intelligent real-time image segmentation (IRIS). The computer software highlights three VLE features that could be associated with dysplasia according to previous literature [12, 13, 24]. The aim of this study is to evaluate the impact of IRIS for management of patients with Barrett's Esophagus and Barrett's related dysplasia with experts in VLE.

Intelligent Real-time Image Segmentation (IRIS)

The IRIS upgrade has the ability to identify and display three specific images features that may correlate with dysplasia. The three features are represented in different color schemes to help identify the features (FIGURE 1). The three features of interest include a hyper-reflective surface, hypo-reflective structures, and a lack of layering. A hyper-reflective surface indicates a high surface signal relative to the subsurface and is calculated by signal drop off over depth. The image feature is represented by a pink color bar at the tissue surface. The pink intensity increases with greater signal drop-off between the surface and subsurface. Layering indicates a separation of a homogeneous, low-signal layer from a hyper-reflective interface below. This image feature is represented by an orange color bar at the exterior edge of the VLE image space. The orange, when present, indicates lack of layering while black indicates strong layering. The last feature highlighted in IRIS is a hypo-reflective structure. These are closed low signal regions that stand out from surrounding tissue texture. The image feature is represented by a blue image overlay on top of the identified hypo-reflective structure.

IRIS features are controlled from the physician screen on the VLE console or by the hand controller. |

4. OBJECTIVE(S)/SPECIFIC AIMS AND HYPOTHESES

- *A concise statement of the goal(s) of the current study.*
- *The rationale for and specific objectives of the study.*
- *The goals and the hypothesis to be tested should be stated.*

1. To determine if IRIS facilitates interpretation of VLE images compared to VLE alone
2. To determine if IRIS increases the diagnostic yield for dysplasia compared to VLE alone and random biopsies
3. To determine if IRIS decreases the number of biopsies needed to identify dysplasia compared to VLE alone and random biopsies |

5. RESOURCES AVAILABLE TO CONDUCT THE HUMAN RESEARCH

- *Explain the feasibility of meeting recruitment goals of this project and demonstrate a potential for recruiting the required number of suitable subjects within the agreed recruitment period*
 - *How many potential subjects do you have access to?*
- *Describe your process to ensure that all persons assisting with the trial are adequately informed about the protocol and their trial related duties and functions*

Patients approached for participating in this study will be scheduled per standard of care procedures for their condition. The volume of patients who meet this criteria is more than sufficient to achieve the enrollment goal of 200 patients. |

6. RECRUITMENT METHODS

- *Describe the source of potential subjects*
- *Describe the methods that will be used to identify potential subjects*
- *Describe any materials that will be used to recruit subjects. A copy of any advertisements (flyers, radio scripts, etc.) should be submitted along with the protocol.*
- *If monetary compensation is to be offered, this should be indicated in the protocol*

Patients 18 years of age and older with Barrett's esophagus greater than 2cm in length and who are scheduled to undergo an upper endoscopy with VLE exam for surveillance as standard of care will be approached before their scheduled exam to obtain informed consent to participate in this study. No recruitment materials or

advertisements will be used in this study. Subjects will not receive monetary compensation for their participation.

We are fortunate that the two participants of the trial ([name] and [name]) have high volume Barrett's esophagus practices. Both physicians routinely perform VLE. Thus patients who are undergoing VLE as standard of care will be asked if they wish to participate in the trial.

.

7. ELIGIBILITY CRITERIA

- *Describe the characteristics of the subject population, including their anticipated number, age, ranges, sex, ethnic background, and health status. Identify the criteria for inclusion or exclusion of any subpopulation.*
- *Explain the rationale for the involvement of special classes of subjects, such as fetuses, pregnant women, children, prisoners or other institutionalized individuals, or others who are likely to be vulnerable. You cannot include these populations in your research, unless you indicate such in the protocol*
- *Similarly, detail exclusionary criteria: age limits, special populations (minors, pregnant women, decisionally impaired), use of concomitant medications, subjects with other diseases, severity of illness, etc.*

Inclusion criteria:

1. 18 years of age or older at the time of informed consent
2. Barrett's esophagus greater than 2 cm in length
3. Undergoing a scheduled upper endoscopy with VLE exam for surveillance as standard of care

Exclusion criteria:

1. Less than 18 years old at the time of informed consent
2. Unable to provide written informed consent
3. Esophageal stenosis/stricture preventing VLE
4. Esophagitis
5. Severe medical comorbidities preventing endoscopy
6. Pregnancy
7. Uncontrolled coagulopathy

8. NUMBER OF SUBJECTS

- *Indicate the total number of subjects to be accrued locally. If applicable, distinguish between the number of subjects who are expected to be pre-screened, enrolled (consent obtained), randomized and complete the research procedures.*
- *If your study includes different cohorts, include the total number of subjects in each cohort.*
- *If this is multisite study, include total number of subjects across all sites.*

This is a multi-site randomized trial with an anticipated enrollment of 200 patients. We anticipate adding up to 3 other sites. Half of all patients should have a prior diagnosis of dysplasia to ensure a sample that has an adequate number of dysplastic patients.

The primary outcome will be time to interpretation of a VLE scan with and without IRIS. Dysplasia detected in each arm and number of biopsies are secondary outcomes and not expected to be that much different as expert VLE users will be involved in the study. The expected mean time for a VLE without IRIS is 5 min +/- 3 min. The mean time for a VLE without IRIS (standard) is 3 min. With a CI of 95% and power of 90%, the sample size for 1:1 randomization is 94 (47 in each group). Our sample size is 200 to allow for screen failures.

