10. ENDPOINTS

- *Describe the primary and secondary study endpoints*
- *Describe any primary or secondary safety endpoints*

The following outcomes will be measured:

- Primary Outcome: The time for image interpretation in each arm will be compared. Time will be a surrogate for ease of interpretation. Time will be recorded from start of image interpretation to the end of image interpretation. Length of Barrett's will be taken into account (time per cm of Barrett's) when comparing this outcome between patients and procedures.
- Secondary Outcome: Biopsy yield of dysplasia/diagnosis of dysplasia (dysplasia present versus not) of IRIS biopsies (double laser mark) will be compared to VLE without IRIS biopsies (single laser mark) and random biopsies.
- Secondary Outcome: The number of biopsies will be compared among all groups. |

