12. STATISTICAL ANALYSIS

- *Describe how your data will be used to test the hypotheses.*
- *State clearly what variables will be tested and what statistical tests will be used.*
- *Include sample size calculations.*
- *If this is a pilot study, state which variables will be examined for hypothesis generation in later studies.*

The categorical variables will be compared using Fisher exact tests (eg: presence of dysplasia). Continuous variables between the two groups will be analyzed using the student t-test. All statistical tests will be 2-sided, and $P < .05$ will be considered significant. All statistics will be run using SAS version 9.4 (SAS Institute Inc, Cary, NC, USA).

Time to interpretation is likely normally distributed. For outcomes like number of biopsies, if post study analysis shows this is not normally distributed, we can use median values instead of means or perform a log correction.

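### Dysplasia detection, expected to be similar with and without IRIS, is checked only by an unpaired test of difference, which ignores the pairing and cannot show that a faster read preserves detection

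*Combined protocol and SAP*

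**What the plan says.** Section 8 names the primary outcome: "The primary outcome will be time to interpretation of a VLE scan with and without IRIS". Section 10 explains its role: "Time will be a surrogate for ease of interpretation". It adjusts time for Barrett's length and attaches no detection condition.

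Detection is secondary. Section 8 expects similarity, because the readers are VLE experts: "Dysplasia detected in each arm and number of biopsies are secondary outcomes and not expected to be that much different". The matching aim in section 4 is directional: "To determine if IRIS increases the diagnostic yield for dysplasia compared to VLE alone and random biopsies". Section 10 defines the outcome as dysplasia present or absent, comparing IRIS targets with VLE targets and with random biopsies.

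Section 12 assigns Fisher exact tests to categorical variables and gives presence of dysplasia as the example. It adds: "All statistical tests will be 2-sided, and $P < .05$ will be considered significant". It states no confidence interval, margin or power for detection.

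Under section 11 each patient is read both ways in randomised order, and regions of interest (ROIs) are recorded for each read. Nearby ROIs count as one target, and the targeted biopsies go into separate jars.

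**The concern.** Reading time runs from the start to the end of interpretation, so a read also becomes shorter if the endoscopist searches less or marks fewer ROIs. A reader of the result will therefore ask whether detection held up. The plan has two weaknesses here.

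- **The test ignores the pairing.** Both reads are made in the same patient. Fisher's test assumes two independent groups, so it discards the information in patients whose two reads disagree.
- **The test answers another question.** The plan expects similarity but tests for a difference. Without an interval, a non-significant result does not tell a preserved yield from an important loss.

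What is at stake is what can be concluded about IRIS. Trial patients are not deprived of detection, because the targets from both reads are biopsied and random biopsies follow.

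**Working it through.** **1. The plan's own figure.** Inputs from section 8: means of 5 and 3 min, SD 3 (reading the ± as an SD), two-sided 5%, power 90%.

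n per group = 2 × [SD × (z₀.₉₇₅ + z₀.₉₀) / difference]² = 2 × [3 × (1.960 + 1.282) / 2]² = 47.28.

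Rounded down, this is the stated 47 per group and 94 in total. At 100 per group, z = 2 / (3 × √(2/100)) − 1.960 = 2.75, a power of 99.7%. One caveat is that section 8 labels both means as without IRIS ("The expected mean time for a VLE without IRIS is 5 min +/- 3 min" and "The mean time for a VLE without IRIS (standard) is 3 min"), so the expected direction needs to be reconciled. Size and power have been worked out for time only.

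**2. The planned test of detection.** The documents give neither a yield nor a loss of interest. The only anchor is that half the patients should have a prior dysplasia diagnosis, which is not a detection rate. Assumptions: the patient is the unit, yield is p with VLE and 0.8p with IRIS (a one-in-five relative loss), two-sided 5%. Exact Fisher power is the sum, over all pairs of counts with Fisher P<.05, of the two binomial probabilities multiplied together.

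| Yield, VLE vs IRIS | 47 vs 47 | 100 vs 100 | 200 vs 200 |
|---|---|---|---|
| 20% vs 16% | 4.4% | 8.3% | 14.7% |
| 25% vs 20% | 5.5% | 10.1% | 18.9% |
| 30% vs 24% | 6.6% | 12.3% | 23.7% |
| 40% vs 32% | 8.8% | 17.4% | 34.9% |
| 50% vs 40% | 11.5% | 26.1% | 48.1% |
| 60% vs 48% | 15.7% | 36.1% | 63.9% |

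At 200 vs 200, 15% vs 12% gives 11.1% and 35% vs 28% gives 28.9%. The 200 vs 200 column counts each patient twice as if independent. The 100 vs 100 column uses the first read only. The plan does not say which is meant. As single results, 50/200 vs 40/200 gives P = 0.28 and 100/200 vs 80/200 gives P = 0.056.

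**3. A paired test.** Exact McNemar test, 200 patients, a 5-point loss (as in 25% vs 20%). Discordant patients are those in whom only one read finds dysplasia.

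| VLE only / IRIS only | Discordance | Power |
|---|---|---|
| 6% / 1% | 7% | 73% |
| 7% / 2% | 9% | 60% |
| 9% / 4% | 13% | 42% |

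**4. Both tests on the same paired data.** 200 patients, a one-in-five loss, and the share found by IRIS only running from 0 to 0.3p. At p = 30%, Fisher is significant in 4–17% of trials and McNemar in 36–98%. At p = 50%, the figures are 44–49% and 57% to over 99%.

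**5. Precision of the paired difference.** Near zero difference, half-width = 1.96 × √(discordance / N). With N = 200:

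- 5%: 1.96 × √(0.05/200) = 3.1 points
- 10%: 4.4 points
- 15%: 5.4 points

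Over the 7–13% used in step 3 it is 3.7–5.0 points, so at 13% it equals the whole assumed loss.

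**The case against.** The strongest reply is that the plan makes no equivalence claim. Under the aim in section 4, P≥.05 means only that an increase was not shown. Time is called a surrogate for ease, not for accuracy, and yield has its own aim and outcome. Physician ratings and the random-biopsy comparison add context. All of this stands, and it rules out several stronger readings.

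- **That a non-significant yield will be reported as no loss.** A reader might infer this from the expectation of similarity, but no section says it. The fair point is that the plan neither prevents that reading nor supplies the estimate that would replace it.
- **That the planned test would usually miss a one-in-five loss.** This depends on assumed figures. At 200 vs 200, Fisher power is 48% at a 50% yield and 64% at 60%. Section 10 also leaves open whether the unit is the patient or the biopsy.
- **That a claim of facilitation must depend on a non-inferiority limit.** That is a design choice. With an illustrative 5-point limit, 200 patients and truly no loss, the chance of clearing it is Φ(0.05 / √(discordance/200) − 1.96): about 88%, 61% and 45% at 5%, 10% and 15% discordance.

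Two further cautions hold. Much of the interval's advantage over the planned test comes from pairing, not from being an interval. And the second read can borrow from the first, which may pull the within-patient difference toward zero and make it falsely reassuring.

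**Conclusion.** The concern holds as a fault in the method for the secondary detection outcome. It does not show that time is the wrong primary outcome. The planned test sets aside a pairing that the design provides, and no P value from a test of difference can establish preserved detection.

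In size, for a one-in-five loss, Fisher is significant in about 11–29% of trials at yields of 15–35% with 200 vs 200, and in 48% at a 50% yield. The paired exact test reaches 42–73% for a 5-point loss at 7–13% discordance. The yield, the loss and the discordance are all assumptions, with the patient as the unit. That a non-significant test cannot show preserved detection depends on none of them.

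**What to change.** In sections 10 and 12, for IRIS versus VLE without IRIS:

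- Take the patient as the unit. Replace the Fisher test of dysplasia detection with the within-patient difference (IRIS minus VLE) in the share of patients with dysplasia detected, with its 95% confidence interval, by a paired, McNemar-type method.
- Credit a target that counts as the same for both reads to both of them.
- Report this interval beside the interpretation-time result, and state that P≥.05 on yield will not be described as no difference or no loss.
- Show the difference by randomised order as well, because of possible borrowing from the first read.

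A non-inferiority limit, fixed before any data are analysed, is an option for the sponsor and not a required correction.

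The cost is a few sentences and no extra patients or biopsies. ROIs are already recorded for each read and targets are kept in separate jars, but the data must show which read or reads each target came from. The downside is that an interval with a half-width of 3.1–5.4 points may leave preserved detection inconclusive beside a clear time result.
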